#### 9.1.6 SUMMARIES OF TREATMENT-EMERGENT ADVERSE EVENTS

TEAEs will be summarized by period based on the SAF.

A brief, high-level summary table will be presented to provide the number and percentage of subjects experiencing any TEAEs, any severe TEAEs, any drug-related TEAEs, any TESAEs, any drug-related TESAEs, any TEAEs leading to study drug interruption or discontinuation, and death.

In addition to the above summary table, summary tables and listings of AE described below will be provided by period.

- Summary of TEAEs by SOC and PT
- Summary of TEAEs by SOC, PT and maximum severity
- Summary of severe (CTCAE Grade  $\geq 3$ ) TEAEs by SOC and PT
- Summary of related TEAEs to Study Treatment by SOC and PT
- Summary of TEAEs of Clinical Interest by SOC and PT
- Summary of related AEs to Study Procedure by SOC and PT
- Summary of serious TEAEs by SOC and PT
- Summary of TEAEs Leading to Premature Discontinuation by SOC and PT
- Summary of related TEAEs to Study Treatment by SOC and PT
- Summary of related Serious AEs to Study Procedure by SOC and PT
- Listing of all AEs
- Listing of serious TEAEs and death
- Listing of TEAEs leading to study drug interruption or discontinuation

#### 9.2 PHYSICAL EXAMINATION

A complete physical examination is performed at the screening visit and end of treatment visits. An abbreviated or targeted interim physical exam may be done to assess areas with previously noted abnormalities and/or that are associated with any new complaints from the subject. All abnormal findings will be presented in a by-subject listing.

### 9.3 VITAL SIGNS

Descriptive statistics will be provided by treatment group for vital signs (blood pressure (mm Hg), heart rate (bpm), respiratory rate, temperature, and weight (kg), as follows:

- Baseline values
- Values at each post-baseline visit
- Change from baseline at each post-baseline visit

A by-subject listing of vital signs will be provided by treatment group, subject ID number, and visit in chronological order.

### 9.4 CLINICAL LABORATORY TESTS

Descriptive statistics will be provided by treatment group for each laboratory test (hematology, chemistry, coagulation, and urinalysis) specified in the study protocol as follows:

- Baseline values
- Values at each post-baseline visit
- Change from baseline at each post-baseline visit

Shift tables will be presented by showing change in lab normal range (low, normal, and high) for clinical laboratory values by treatment group.

Laboratory values will be listed in by-subject listings. Laboratory values which fall outside the reference ranges and have clinically significant and abnormal findings will be provided in a separate by-subject listing. These listings will include treatment group, subject ID, laboratory collection date/time, analyte name, analyte finding, and reference range.

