2.2 Endpoints

2.2.1 Primary Endpoint

- Safety and tolerability as assessed by incidence of treatment-emergent adverse events (TEAEs), treatment-emergent serious adverse events (TESAEs), and changes in laboratory values, electrocardiograms (ECGs), physical exam findings, and vital signs through Week 12

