3.1.1.3 Dose-Limiting Toxicity

A dose-limiting toxicity (DLT) is defined as any treatment-related adverse event (AE) reported within 4 weeks from dosing that meets both of the following criteria:

- Grade 3 or higher in severity according to the National Cancer Institute (NCI) Common Terminology Criteria for Adverse Events (CTCAE), Version 5.0
- A shift of ≥ 2 NCI CTCAE grades from baseline (initial presentation of the AE)

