9.3.7.4 Clinical Laboratory Results

Laboratory values (e.g., chemistry, hematology, and urinalysis) may be presented graphically by visit. Summary statistics may be tabulated as appropriate by scheduled visit. Laboratory values will be listed with grade per NCI CTCAE and flagged when values are outside the normal reference range.

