#### 4.3 HANDLING OF DATA

In general, missing data will not be imputed unless methods for handling missing data are specified. For purposes of the DRC safety assessment, all results will be presented ‘as observed’ with missing values not imputed. The handling of missing data in analyses of the efficacy endpoints is discussed in Section 6.2.4.

If multiple valid, non-missing, continuous measurements or visits (regardless if it’s scheduled or unscheduled) occurring within a single visit, records will be chosen based on the following rules if a single value is needed:

- For baseline, the baseline value will be the last non-missing value prior to the first dosing of study drug; if multiple measurements occur on the same day, the last non-missing value prior to the time of first dosing of study drug will be considered as the baseline value. If these multiple measurements occur at the same time or the time is not available, the average of these measurements will be considered the baseline value.
- For post-baseline values:
  - a. The record closest to the nominal day for that visit will be selected.
  - b. If there are 2 records that are equidistant from the nominal day, the later record will be selected.
  - c. If there is more than 1 record on the selected day, the average will be taken.

If multiple valid, non-missing, categorical observations exist for one visit, records will be selected as follow:

- For baseline, the last available record prior to the first dose of study drug will be selected. If there are multiple records at the same time or no time recorded on the same day, the worst value will be selected unless otherwise specified.
- For post-baseline values:
  - a. The record closest to the nominal day for that visit will be selected.
  - b. If there are 2 records that are equidistant from the nominal day, the later record will be selected.
  - c. If there is more than 1 record on the selected day, the value with the worst severity will be used.

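### The planned laboratory shift tables show only low, normal or high, and no summary by CTCAE grade or worst post-baseline value is planned

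*SAP*

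**What the plan says.** Protocol 2.2.1 makes laboratory change part of the primary endpoint: "changes in laboratory values, electrocardiograms (ECGs), physical exam findings, and vital signs through Week 12".

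For the analysis, SAP 9.4 gives three outputs:

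- descriptive statistics by treatment group for each test, as values and as change from baseline at each visit (SAP 4.1 includes minimum and maximum among these statistics);
- shift tables: "Shift tables will be presented by showing change in lab normal range (low, normal, and high", by treatment group;
- listings: "Laboratory values will be listed in by-subject listings", with a separate listing of out-of-range values that are clinically significant.

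On listing content, SAP 9.4 says: "These listings will include treatment group, subject ID, laboratory collection date/time, analyte name, analyte finding, and reference range". Protocol 9.3.7.4 says: "Laboratory values will be listed with grade per NCI CTCAE and flagged when values are outside the normal reference range".

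Where several records fall in one visit, SAP 4.3 says "records will be chosen based on the following rules if a single value is needed", and for post-baseline values: "The record closest to the nominal day for that visit will be selected". Ties in distance go to the later record. Several records on the chosen day are averaged if continuous; if categorical, the worst is taken.

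**The concern.** A table with three categories cannot separate degrees of abnormality. A subject who is already high at baseline and becomes much worse stays in the high-to-high cell. A subject who starts within range and reaches a severe value is counted in the same cell as one who just crosses the limit. The protocol itself works in grades: its dose-limiting toxicity definition needs Grade 3 or higher and a shift of at least two "NCI CTCAE grades from baseline".

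Baseline values outside the range are plausible in active ulcerative colitis. Under Protocol 4.2 (criterion 8), hemoglobin below 8.5 g/dL excludes a subject only as one of at least four features of a symptom complex, so a low hemoglobin does not in itself exclude. Eosinophils matter as well: Protocol 1.3 reports mild eosinophilia among the most common adverse events in the healthy-subject multiple-dose study.

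Record selection can add to the problem. If one record per visit feeds these tables, a worse value drawn some days from the nominal day can be passed over. What is at stake is whether a reader can see from a table, by dose, how many subjects worsened and how far.

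**Working it through.** The plan states no figure on this point, so there is none to reproduce. The check has three parts.

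**1. What the three categories can show.** Take grades 0 to 4 in one direction (all high or all low). Assumption: Grade 0 is within range and Grade 1 or above is outside it. This may not hold for an analyte whose grading does not start at the limit of the range.

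- Worsening transitions: pairs (a, b) with a < b, giving 5 × 4 / 2 = 10.
- A transition changes category only if a = 0: 0→1, 0→2, 0→3, 0→4. That is 4 of 10, all in one cell.
- No change of category: 1→2, 1→3, 1→4, 2→3, 2→4, 3→4. That is 6 of 10.
- Transitions that meet the grade test in Protocol 3.1.1.3 (b ≥ 3 and b − a ≥ 2): 0→3, 0→4, 1→3, 1→4, 2→4, so 5. Of these, 1→3, 1→4 and 2→4 show as no shift: 3 of 5.
- With a table of baseline grade against worst post-baseline grade, 10 of 10 and 5 of 5 would show.

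These are counts of possible transitions. They do not say how often each would occur.

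**2. What the single-record rule would do if applied.** Example with assumed values: nominal Day 29, scheduled eosinophil count 1.0 giga/L on Day 29, unscheduled count 5.5 giga/L on Day 32. The distances are |29 − 29| = 0 and |32 − 29| = 3, so the rule keeps 1.0. If the worst of m records in a window is equally likely to be any of them (assumption), it is kept with probability 1/m: 50% for m = 2, 33% for m = 3, 25% for m = 4.

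**3. Which abnormalities other outputs would count.**

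| Route | What it covers | What it leaves |
|---|---|---|
| Adverse event tables (SAP 9.1.6; recording rule in Protocol 7.6.1.1) | Laboratory abnormalities that are symptomatic, need intervention, are serious, or lead to study termination or to interruption or discontinuation of treatment | Asymptomatic values with no action taken |
| SAP 9.6 counts | ALT and AST at 3 × ULN or more; bilirubin at 2 × ULN or more with alkaline phosphatase below 2 × ULN; overdose | Every non-hepatic analyte, including eosinophils |
| By-visit minimum and maximum (SAP 4.1) | Group extremes among the records used | Number of subjects affected and link to their own baseline |
| Listings (SAP 9.4) | Every value, with date and reference range | Grade, and any count by dose |

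Asymptomatic, non-hepatic worsening that prompts no action is therefore not counted by severity in any planned table. On scale, Protocol 9.1 plans 8 PT101 subjects per dose level, so one subject is 1/8 = 12.5% of a group.

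The listing discrepancy needs no arithmetic. Protocol 9.3.7.4 includes the CTCAE grade, the fields named in SAP 9.4 do not, and the four changes recorded in SAP 14 do not mention it.

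**The case against.** The strongest reply is that little is really lost. Every laboratory value is listed, and with about 8 PT101 subjects per dose the listings can be read subject by subject. The descriptive statistics carry a minimum and maximum, so a selected eosinophil value of 6.0 giga/L would not look like 1.6. The protocol promised grade only in listings, so the shift table is already an addition to it, in a safety analysis with no inferential testing. All of this stands, and it limits the point. It does not supply a count of subjects by severity and dose.

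A reader might infer more than the documents support:

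- *That the worst unscheduled values drop out of the primary endpoint.* They stay in the listings. The SAP 4.3 rule is conditional on one value being needed, SAP 9.4 gives no time basis for the shift table, and scheduled and unscheduled records compete on equal terms. Applying the rule here is the likely default but is not stated.
- *That dose-limiting toxicities would be missed.* These are treatment-related adverse events, assessed on adverse event data and listed separately (SAP 13 and 13.1). The shift table does not determine them.
- *That the Data Review Committee would be misled by the shift tables.* SAP 13 does not name them in its package. It names laboratory descriptive statistics, adverse events by maximum severity, and the listing of dose-limiting toxicities.
- *That severe eosinophilia would go unseen.* A confirmed count above 5.0 giga/L ends dosing (Protocol 3.1.7). An abnormality that ends dosing is recorded as an adverse event (Protocol 7.6.1.1) and so reaches the tables in SAP 9.1.6, which also include one for events of clinical interest. What can escape is a raised count that does not meet the confirmation or recurrence conditions and prompts no action.

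**Conclusion.** The point holds as a gap in presentation with a cheap remedy. The shift tables in SAP 9.4 cannot show worsening in a subject already out of range in that direction at baseline (6 of 10 worsening transitions), and they do not rank severity among subjects who start within range. This rests on equating Grade 0 with within range. No worst post-baseline or graded laboratory summary fills the gap, although laboratory change belongs to the primary endpoint.

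The practical effect is confined mainly to asymptomatic, non-hepatic abnormalities without action. The 12.5% is the weight of one subject in a dose group; it does not estimate how many would be missed. The loss of records from by-visit summaries depends on the single-record rule being applied to these tables.

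The omission of the CTCAE grade from the listing fields is a plain difference between protocol and SAP that SAP 14 does not record.

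**What to change.** Amend the SAP as follows:

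1. In 9.4, add a shift table by dose group from baseline CTCAE grade to worst post-baseline CTCAE grade through Week 12, for analytes that have CTCAE criteria. Use all scheduled, unscheduled and repeat values. The low/normal/high table can stay.
2. Add counts of subjects by maximum eosinophil count, at the protocol's existing cut-points of 1.5 and 5.0 giga/L. This is for display only and changes no stopping rule. The bands in Protocol 3.1.7 leave a value of exactly 5.0 in neither, so the table should state its own boundary.
3. In 4.3, state that for laboratory data the nearest-nominal-day rule applies only to by-visit summaries.
4. Restore the CTCAE grade to the laboratory listing, or record its removal in SAP 14.

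The cost is SAP text, standard programming and one more set of tables to review. No new data and no change at the sites are needed.

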### 9.5 ELECTROCARDIOGRAMS

Triplicate ECG measurements will be obtained at the screening visit and on Day 1. On Day 1 only, triplicate ECGs will be performed ~ 12 hours after study drug administration. The median of these measurements will be used to calculate change from baseline for safety evaluations. The ECG assessment values at each visit and change from baseline to each visit will be summarized and shift tables using the normal/abnormal classification to compare baseline to the post-baseline visit values will be provided. In addition, a by-subject listings, which includes treatment group, subject ID, ECG date/time, test name, test result, and ECG interpretation (e.g., clinical interpretation such as normal, abnormal – not clinically significant, abnormal – clinically significant) will be presented. If any clinically significant ECG measurement occurs, it will be recorded as an AE.

### 9.6 EVENTS OF CLINICAL INTEREST

The number and percentages of subjects with the following elevations in hepatic laboratory tests and drug overdoses will be summarized between treatment groups and included in a by-subject listing.

- An overdose of study product, defined as any dose of any drug administered as part of the study exceeding the dose prescribed by the protocol.
- ALT  $\geq 3x$  upper limit of normal (ULN)

- AST  $\geq$  3x ULN
- Total bilirubin level (TBL)  $\geq$  2xULN and alkaline phosphatase value  $<$  2xULN

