7.6.1.6 Events of Clinical Interest

Selected serious and nonserious AEs are also known as ECIs and must be reported to the Sponsor.

ECIs for this study include:

1. An overdose of Sponsor's product, as defined in [Section 7.6.1.7](#)
2. An elevated AST or ALT laboratory value that is greater than or equal to 3X the ULN and an elevated total bilirubin laboratory value that is greater than or equal to 2X the ULN and, at the same time, an alkaline phosphatase laboratory value that is less than 2X the ULN, as determined by way of protocol-specified laboratory testing or unscheduled laboratory testing.*

*Note: These criteria are based on available regulatory guidance documents. The purpose of the criteria is to specify a threshold of abnormal hepatic tests that may require an additional evaluation for an underlying etiology. The study-site guidance for assessment and follow up of these criteria can be found in [Appendix 7](#) and in the Investigator Study File Binder (or equivalent).

It may also be appropriate to conduct additional evaluation for an underlying etiology in the setting of abnormalities of liver blood tests including AST, ALT, bilirubin, and alkaline

phosphatase that do not meet the criteria noted above. In these cases, the decision to proceed with additional evaluation will be made through consultation between the study investigators and the Sponsor. However, abnormalities of liver blood tests that do not meet the criteria noted above are not ECIs for this study.

3. Skin rash or pruritis being rated by the Investigator as Grade 3 in intensity
4. Dyspnea, all intensities
5. Significant eosinophilia defined as AEC > 5.0 giga/L confirmed on repeat measurement after at least 24 hours or eosinophil-associated organ injury.

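### SAP 9.6 replaces the protocol's single concurrent hepatic event of clinical interest with separate test lines, so its rows include non-events and do not give the number of subjects meeting the criterion

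*SAP*

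**What the plan says.** Protocol 7.6.1.6 lists five ECIs and describes them as selected adverse events that must be reported to the sponsor:

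1. Overdose.
2. One hepatic criterion: an aminotransferase elevation, a bilirubin elevation and, "at the same time, an alkaline phosphatase laboratory value that is less than 2X the ULN".
3. A skin criterion: "Skin rash or pruritis being rated by the Investigator as Grade 3 in intensity".
4. Any dyspnea, whatever its grade.
5. An eosinophil criterion: "Significant eosinophilia defined as AEC > 5.0 giga/L confirmed on repeat measurement after at least 24 hours or eosinophil-associated organ injury".

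On liver tests the section also sets a limit: "abnormalities of liver blood tests that do not meet the criteria noted above are not ECIs for this study".

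SAP 9.6 carries the same heading as the protocol section. Its scope is "The number and percentages of subjects with the following elevations in hepatic laboratory tests and drug overdoses will be summarized between treatment groups", and the sentence goes on to promise a by-subject listing. Four bullets follow: overdose; ALT ≥3×ULN; AST ≥3×ULN; and total bilirubin ≥2×ULN with alkaline phosphatase <2×ULN.

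Two other SAP outputs bear on the point. Section 9.1.6 plans a table titled "Summary of TEAEs of Clinical Interest by SOC and PT" and does not say which events enter it. Section 9.4 says "Shift tables will be presented by showing change in lab normal range (low, normal, and high) for clinical laboratory values by treatment group", and adds by-subject laboratory listings.

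**The concern.** The SAP section that carries the ECI heading does not use the protocol's hepatic definition. A subject with an isolated ALT of 3×ULN is counted there, although the protocol says such a finding is not an ECI. A subject with raised ALT at one visit and raised bilirubin at another appears on two lines without meeting the concurrent criterion. No row counts the subjects who do meet it.

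Safety is the primary objective, and SAP section 9 evaluates it by descriptive statistics without inferential testing. The counts by treatment group are therefore the result. Protocol Appendix 7 treats the concurrent hepatic criterion as the laboratory signal of a potential Hy's Law case, so a reader of the study report would look for that count. Under the current text it would have to be assembled afterwards from listings rather than by a prespecified rule.

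The eosinophil ECI raises a smaller version of the same question, because no planned summary row is explicitly set at its threshold. The signal is foreseeable: Protocol 1.3 names mild eosinophilia among the most common adverse events in the concurrent healthy-subject study.

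**Working it through.** The plan states no figure to reproduce. The check is a comparison of the two lists, followed by two short counts.

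**Item by item**

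| Protocol 7.6.1.6 | SAP 9.6 | Other SAP summaries by group |
|---|---|---|
| Overdose | Same definition | – |
| Hepatic: (ALT or AST ≥3×ULN) and bilirubin ≥2×ULN and concurrent ALP <2×ULN | Three separate lines; 0 of 3 join an aminotransferase to bilirubin, 0 of 3 state concurrence | 9.1.6 by preferred term; 9.4 low/normal/high shifts |
| Grade 3 rash or pruritus | Outside its stated scope | 9.1.6 ECI table, and tables by severity |
| Dyspnea, any grade | Outside its stated scope | 9.1.6 ECI table, and all-TEAE table |
| Confirmed AEC >5.0 giga/L, or eosinophil-associated organ injury | Outside its stated scope | 9.1.6 ECI table by preferred term; 9.4 low/normal/high shifts |

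**Could the SAP 9.6 bullets be read jointly?** Joining all of them would require ALT and AST both to be raised, where the protocol requires either, and would also require an overdose. Neither a separate nor a joint reading gives the protocol criterion.

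**How far the two rules differ.** Take four yes/no conditions: A (ALT ≥3×), B (AST ≥3×), C (bilirubin ≥2×), D (ALP <2×). There are 2⁴ = 16 combinations.

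- Protocol criterion, (A or B) and C and D: 3 × 1 × 1 = 3 combinations.
- At least one SAP line, A or B or (C and D): A or B holds in 3 × 4 = 12 combinations. Neither A nor B, but C and D, adds 1. Total 13.
- So 13 − 3 = 10 combinations put a subject under the ECI heading without an ECI.

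These are logical combinations, not frequencies. They show how the rules differ, not how often subjects would be misclassified.

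**Whether the rows give the criterion count.** Let a, b and c be the subjects on the ALT, AST and bilirubin/ALP lines among n, and let u be the number on the ALT or AST line, which lies between max(a, b) and min(n, a + b). The number on both an aminotransferase line and the bilirubin/ALP line lies between max(0, u + c − n) and min(u, c). Take n = 8, the planned PT101 number per cohort, with assumed row counts:

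- a = b = c = 1: u is 1 or 2, so 0 or 1 subjects.
- a = b = c = 2: u is 2 to 4, so 0 to 2 subjects.

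The lines also carry no timing, so being on both does not establish concurrence. The rows bound the answer from above only: if the bilirubin/ALP row is zero, so is the criterion count.

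**The eosinophil ECI.** Protocol 3.1.7 gives three eosinophil routes to stopping: confirmed AEC >5.0 giga/L; persistent AEC between 1.5 and 5.0 giga/L; and any new confirmed elevation above ULN with suspected organ injury. All three can produce adverse events. A table by SOC and preferred term has no AEC cut-off to separate them, and a low/normal/high shift puts all of them in the high category. The organ-injury arm can fall under any of the seven organ systems that Protocol 3.1.7 names, so it has no single preferred-term row either.

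**The case against.** The strongest reply is that SAP 9.6 is not the only ECI output. Its opening sentence limits it to liver tests and overdose, and SAP 9.1.6 plans a separate table of TEAEs of clinical interest. The protocol defines ECIs as adverse events. Protocol 7.6.1.1 generally keeps bare laboratory abnormalities out of the adverse event record, but makes an exception when they lead to discontinuation of treatment. Both the hepatic criterion and confirmed AEC >5.0 giga/L are permanent-discontinuation rules in Protocol 3.1.7, so both should enter the adverse event data. If the 9.1.6 table uses the protocol's definition, ECI status itself applies the threshold. The listings in SAP 9.4 and 9.6 give values by subject, in 9.4 with collection date and time, and with about 60 subjects a tally by hand is feasible. Protocol 9.3.7 promises no ECI summary, so the absence of an ECI entry among the four changes in SAP section 14 shows little. Separate ALT and AST counts are also more inclusive than the combined criterion, so they do not hide a liver signal.

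Most of this stands. A reader might infer that the SAP drops three of the five ECIs, or that no output captures them. The documents do not support that, for the reasons just given. Dyspnea and Grade 3 rash or pruritus are also visible in the ordinary TEAE and severity tables. Nor can a reader infer that cases would be missed: ECIs are reported on the SAE timeline (Protocol 7.6.1.4), and hepatic cases stop treatment and are worked up individually (Protocol 3.1.7 and Appendix 7).

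Two things are not answered. The 9.1.6 table is never tied to Protocol 7.6.1.6, and the only SAP section that spells out ECIs is 9.6, whose hepatic rule differs. And even when correctly populated, a SOC and preferred-term table has no row for the concurrent hepatic criterion.

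**Conclusion.** The concern holds as a reporting mismatch, at minor to should-fix level. Three parts are established from the text:

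- SAP 9.6 applies a different hepatic rule from Protocol 7.6.1.6 and counts, under an ECI heading, findings the protocol says are not ECIs.
- Its summary rows do not give the number of subjects per group who meet the concurrent criterion.
- The 9.1.6 ECI table has neither an event list nor a protocol reference, and no row is explicitly set at confirmed AEC >5.0 giga/L.

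The wider inference, that rash, dyspnea and eosinophilia ECIs go unreported or that safety monitoring is weakened, is not supported. Those events can reach the adverse event tables, and detection, stopping and expedited reporting do not depend on SAP 9.6. The DRC safety outputs listed in SAP section 13 do not name the 9.6 rows either.

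The conclusion assumes that the SAP 9.6 bullets are programmed as written, as separate rows. The documents do not say whether the adverse event data carry an ECI flag. If they do, and the 9.1.6 table uses it with the protocol definition, the eosinophil gap narrows to the lack of an explicit row. The hepatic mismatch in 9.6 remains.

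**What to change.** - In SAP 9.6 and 9.1.6, cite Protocol 7.6.1.6 as the ECI list, so that both outputs use one definition.
- Add a row by treatment group for subjects meeting the concurrent hepatic criterion, evaluated on results from the same time point.
- Add a row by treatment group for confirmed AEC >5.0 giga/L or eosinophil-associated organ injury.
- Keep the single-test ALT, AST and bilirubin/ALP counts as supportive laboratory summaries, not labelled as ECIs.

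The cost is a few lines of SAP text and two table rows. No new data are needed, and neither trial conduct nor any clinical rule changes.
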